3.6. Adjustments for Covariates

Due to small sample size, no formal statistical analyses that adjust for possible covariate effects are planned. Exploratory subgroup analyses may be performed for descriptive purposes.

3.7. Multiple Comparisons/Multiplicity

Multiplicity is not of concern for this study where Stages 1 and 2 were hypothesis generative cohorts. Stage 3A has a single primary efficacy endpoint: to analytically evaluate the clinical benefit derived from individual components, or variations thereof, of the MDS/MPN 2015 criteria. Additional endpoint analysis will be exploratory.

Type I error control will not be applied.

3.8. Subpopulations

Exploratory subgroup analyses may be performed for descriptive purposes.

3.9. Withdrawals, Dropouts, Loss to Follow-up

Patients who are withdrawn or discontinue from the study will not be replaced.

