7.2 Replacement of Patients

At the discretion of the Sponsor, additional patients may be enrolled to provide sufficient patient data for analysis after a patient prematurely withdraws from the study.

8 Treatment of Subjects

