In this exploratory stage, the primary evidence of activity in each subset would be (1) a reduction in spleen volume that correlates with an improvement in symptom score or (2) conversion from transfusion-dependent to transfusion-independent. These occurrences on a per-patient basis would be considered responses within each subgroup. Clinical activity would have been demonstrated if at least 1 patient achieves either of these clinically important outcome responses. Up to 5 additional patients with either of these specific baseline characteristics may be enrolled in Stage 3A, to increase the confidence in the observed results, if necessary. It can be seen in the graph below that for any true rate of response that is ≥ 0.15 , this approach would have at least 80% power to detect at least one responder. Given at least a single responder, additional methods such as confidence interval estimation or formal power calculations, may be used to determine whether to move ahead with a confirmatory Stage 3B.

The operating characteristics of this approach to sample size estimation in Stage 3A may be seen in the following graph. This graph presents the sample size required to have either an 80%, 90%, or 95% probability of at least 1 responder when the sample size is N, and the true probability of response is P.

As an example, if the true response probability were 0.15, 10 patients evaluated for a given response type would result in at least one response with 80% probability.

Other subsets of patients may be retrospectively identified in which treatment with tagraxofusp may result in clinically important outcomes, and enrichment strategies within the framework of this sample size may be applied, with the same objective of rejecting a meaningless rate of clinical activity.

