3.1.2. Stage 3A Sample Size Justification

Approximately 20 patients with CMML may be enrolled in each of the two cohorts in Stage 3A to ensure a sufficient number of patients with specific baseline disease characteristics are enrolled to reject a meaningless rate of clinical activity in subsets of interest. (For our purposes, a meaningless rate will be taken to mean that there are no responders, using the definitions below, in the sample for each of the following subsets.) No formal stratification will be performed; however approximately 8-10 patients with baseline splenomegaly (defined as ≥ 5 cm below the left costal margin) and approximately 8-10 patients who are transfusion-dependent at baseline (receipt of at least 4 transfusions within 8 weeks before the first tagraxofusp dose) will be included in each 20-patient cohort. This intended enrollment distribution may be adjusted, depending on the actual prevalence of splenomegaly and transfusion-dependence seen in the general patient population as the study continues to enroll.

In this exploratory stage, the primary evidence of activity in each subset would be (1) a reduction in spleen volume that correlates with an improvement in symptom score or (2) conversion from transfusion-dependent to transfusion-independent. These occurrences on a per-patient basis would be considered responses within each subgroup. Clinical activity would have been demonstrated if at least 1 patient achieves either of these clinically important outcome responses. Up to 5 additional patients with either of these specific baseline characteristics may be enrolled in Stage 3A, to increase the confidence in the observed results, if necessary. It can be seen in the graph below that for any true rate of response that is ≥ 0.15 , this approach would have at least 80% power to detect at least one responder. Given at least a single responder, additional methods such as confidence interval estimation or formal power calculations, may be used.

The operating characteristics of this approach to sample size estimation in Stage 3A may be seen in the following graph. This graph presents the sample size required to have either an 80%, 90%, or 95% probability of at least 1 responder when the sample size is N, and the true probability of response is P.

As an example, if the true response probability were 0.15, 10 patients evaluated for a given response type would result in at least one response with 80% probability.

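### Protocol and SAP give different rules on replacing withdrawn patients, and the 80% used to size Stage 3A needs 10 evaluated patients with no allowance for fewer

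*SAP*

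**What the plan says.** On withdrawals the two documents differ. SAP 3.9 says: "Patients who are withdrawn or discontinue from the study will not be replaced". Protocol 7.2 says that, at the sponsor's discretion, "additional patients may be enrolled to provide sufficient patient data for analysis after a patient prematurely withdraws from the study". The protocol clause names no cohort, no subset and no criterion for using it. SAP Section 5, which records departures from the planned analyses, is silent on the difference.

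On sizing they agree. Protocol 14.2.2 and SAP 3.1.2 carry the same argument. Each cohort of about 20 is meant to include "approximately 8-10 patients with baseline splenomegaly" and a similar number who are transfusion-dependent. The success rule is: "Clinical activity would have been demonstrated if at least 1 patient achieves either of these clinically important outcome responses". For true rates of 0.15 or more, "this approach would have at least 80% power to detect at least one responder", and the worked example at 0.15 is that "10 patients evaluated for a given response type would result in at least one response with 80% probability". Both also allow that "Up to 5 additional patients with either of these specific baseline characteristics may be enrolled in Stage 3A", to strengthen confidence in the results. Neither gives a dropout rate or inflates the sample for dropout.

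On who is counted, Protocol 14.1 analyses everyone who received any study drug. SAP 2.1 makes the mITT population primary for efficacy. A treated patient with no later efficacy assessment is left out of it unless the reason for stopping was death or progression. SAP 4.3 adds a supportive efficacy analysis in the Safety Population.

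**The concern.** One document permits additions after withdrawal and the other rules out replacement, and no text says which governs. Under an at-least-one-responder rule, each added patient can only raise the chance of declaring activity. In an open-label study with a discretionary top-up, the report should therefore say whether the option was used.

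The sizing statement also depends on the number evaluated. If withdrawn patients are not replaced, a patient lost before evaluation lowers that number, and neither document says what then happens to the 80%. The planned range of 8-10 already starts below 10.

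At stake are the accuracy of a stated operating characteristic and a clear record of who was enrolled and counted. No hypothesis test is affected: SAP 3.7 applies no type I error control.

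**Working it through.** **Inputs.** True response probability P = 0.15, 10 evaluated patients and a stated 80% (Protocol 14.2.2, SAP 3.1.2). Success means at least 1 responder. Planned subset size is 8-10, with up to 5 optional extra patients (both sections). Each response type is taken on its own, as in the documents' worked example.

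**Formula.** With n evaluated patients, P(at least 1 responder) = 1 − (1 − P)^n = 1 − 0.85^n.

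**The plan's own figure.** n = 10: 1 − 0.85^10 = 1 − 0.1969 = 80.3%. The printed 80% is reproduced.

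**Slack.** The smallest n reaching 80% solves 0.85^n ≤ 0.20, so n ≥ ln(0.20)/ln(0.85) = 9.90, that is 10. Ten is the minimum.

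| Evaluated | 1 − 0.85^n |
|---|---|
| 10 | 80.3% |
| 9 | 76.8% |
| 8 | 72.8% |
| 7 | 67.9% |

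The planned 8-10 therefore gives 72.8% to 80.3% if every enrolled patient is evaluated. Reaching 80% with 8 evaluated needs a true rate of 1 − 0.20^(1/8) = 0.182. With 9 it needs 1 − 0.20^(1/9) = 0.164. The statement that 80% holds for any rate of 0.15 or more is thus not met at the lower end of the planned range. These results are given by number evaluated, so they need no assumed dropout rate.

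**Effect of the optional extra patients.**
- 11 enrolled, 1 lost: 10 evaluated, 80.3%.
- 15 enrolled (10 plus all 5 in one subset), none lost: 91.3%.
- 15 enrolled, 3 lost: 12 evaluated, 85.8%.
- 15 enrolled, 5 lost: 10 evaluated, 80.3%.
- From 8 enrolled, 2 extra are needed to reach 10 before any loss.

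The documents do not make clear whether the 5 are per subset or for Stage 3A as a whole.

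**Replacement and denominator, side by side.**
- Protocol: additions permitted (7.2); all treated patients analysed (14.1).
- SAP: no replacement (3.9); primary efficacy in mITT (2.1, 4.3), which can drop a treated patient who leaves unassessed for a reason other than death or progression; supportive efficacy in the Safety Population (4.3).

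**The case against.** The strongest reply is that little turns on this. SAP Section 5 records that Stage 3A enrolment was not continued, Stage 3B was not started, and the Bayesian and correlative analyses were dropped. A permissive protocol clause can simply go unused, and a no-replacement statement fits a closed cohort. That stands: no design decision changes now. It does not tell the reader whether anyone was added while the protocol clause was in force.

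A second reply is that early departure does not always make a patient unevaluable. Protocol Table 4 schedules response assessment at the end of Cycle 1, and marrow and imaging at End of Treatment, including for patients who stop before completing Cycle 4. Stopping for death or progression keeps the patient in mITT. This also stands, with one limit: SAP 1.2.5.1 requires at least 8 transfusion-free weeks on treatment for transfusion independence in CMML, so a patient who leaves earlier cannot meet that definition.

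Two stronger readings are tempting. A reader might infer that the 80% survives dropout only under the protocol's rule. The documents do not support this. The figure is conditional on 10 evaluated patients and is correct under either rule once 10 are evaluated. The optional extra patients are in the SAP too and can restore 10, although replacement is not their stated purpose. Nor does Protocol 7.2 secure 10, being discretionary and not tied to a subset.

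A reader might also infer that replacement inflates the reported response rate by swapping withdrawn patients out of the denominator. That joins the protocol's replacement rule to the SAP's evaluable-only population. The protocol analyses all treated patients, and the SAP, which uses mITT, rules out replacement. The SAP also has a not-evaluable category (4.3.1) and calculates categorical percentages on the total population, including patients with missing results (3.10).

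**Conclusion.** The point holds in a limited form. The replacement rules differ and the difference is not listed in SAP Section 5. The 80% is arithmetically correct for 10 evaluated patients but is the bare minimum. At P = 0.15 the planned 8-10 per subset gives about 73-80% before any loss without the optional extra patients, and each evaluated patient below 10 costs about 3.5 to 5 points over the range 10 to 7. The calculation assumes independent patients with a common response rate. It does not show that either rule makes the printed figure wrong, or that any reported rate is biased. A separate gap remains: the primary mITT population can exclude treated patients who leave unassessed for reasons other than death or progression, which departs from Protocol 14.1. With enrolment stopped and the analysis descriptive, the consequence is for transparency and for the stated operating characteristic.

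**What to change.** (a) Reconcile Protocol 7.2 and SAP 3.9 on no replacement and list the difference in SAP Section 5. State there and in the study report whether any patient was added after a withdrawal and, if so, in which cohort. If anyone was added, correct SAP 3.9 to say so.

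(b) Keep every treated patient in the response-rate denominator and count unassessed early withdrawals as non-responders. This agrees with Protocol 14.1 and can use the Safety Population analysis already planned in SAP 4.3, with mITT shown alongside.

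(c) In SAP 3.1.2, say that 80% at P = 0.15 applies only if 10 patients are evaluable, and that 8-9 evaluable gives about 73-77%. Do not insert a dropout rate, since neither document supports one.

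The cost is a few sentences, a change in which efficacy population leads, and no added patients. The stated probability becomes slightly less favourable, and reported response rates may be slightly lower.

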3.10. Missing, Unused, and Spurious Data

In general, there will be no substitutions made to accommodate missing data points. All data recorded on the eCRF will be included in data listings that will accompany the CSR.

For categorical variables, a category for missing data of the parameter will be presented. Percentages will be calculated from the total population, including patients with missing results.

When tabulating AE data, partial dates will be handled as follows. If the day of the month is missing, the onset day will be set to the first day of the month unless it is the same month and year as study treatment. In this case, in order to conservatively report the event as treatment-emergent, the onset date will be assumed to be the date of treatment. If the onset day and month are both missing, the day and month will be assumed to be January 1, unless the event occurred in the same year as the study treatment. In this case, the event onset will be coded to the day of

treatment in order to conservatively report the event as treatment-emergent. A missing onset date will be set up to the first day of treatment.

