4.3. Efficacy Evaluation

Efficacy analyses will be conducted using the mITT population for patients treated at 12 µg/kg/day. Supportive analysis of efficacy based on the Safety Population will be performed for patients treated at 12 µg/kg/day and patients treated at 7 or 9 µg/kg/day. Efficacy summaries will be presented as described in [Section 3.5](#). Data for all efficacy endpoints will be presented in by-patient listings.

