4.3.1. Response Rate

Objective response rate and the corresponding 95% Clopper Exact CIs will be presented as the number and percentage of patients who achieve disease-specific complete response (CR) or partial response (PR) after treatment.

Best overall response will be presented as the number and percentage of patients who achieve disease-specific (see [Section 8](#)) CR, PR, stable disease (SD), progressive disease (PD) or who are not evaluable (NE) as their best response on study.

Swim lane plots will be produced for each disease presenting the time on treatment and in response.

The time from the date of first infusion of tagraxofusp to the date from when criteria are first met for CR or PR will be summarized.

Patients who remain in response per investigator and receive a stem cell transplant will be identified and summarized.

For MF patients, the number and percentage of patients who achieved clinical improvement, anemia, spleen, or symptom responses, molecular remission, or cytogenetic/molecular relapse will also be presented using IWG-MRT/ELN criteria (see [Section 8.1](#) for disease specific response criteria). The time from date of first infusion of tagraxofusp to the date from when each response of clinical benefit criteria (as defined in Table 8-4 in [Section 8.2](#)) are first met will be summarized.

For CMML patients, the number and percentage of patients who achieved erythroid, platelet, neutrophil, spleen or symptoms responses will also be presented (see [Section 8.2](#) for disease specific response criteria). The time from date of first infusion of tagraxofusp to the date from when each category of clinical benefit criteria are first met will be summarized.

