4.3.5. Spleen Volume

Spleen size by MRI/CT will be summarized over time for all patients with baseline splenomegaly. The number and percentage of patients with $\geq 10\%$, $\geq 25\%$, and $\geq 35\%$ reduction in spleen volume from baseline will be summarized over time.

The maximum percent reduction from baseline in spleen size across all post-baseline visits will be summarized. A waterfall plot of the maximum percent reduction in spleen volume, spleen volume at Cycle 4 Day 21 visit, and spleen volume at Cycle 7 Day 28 will be created.

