4.3.6. Tumor Symptom Score

Symptom scores will be summarized over time for all patients. The number and percentage of patients with $\geq 25\%$ and $\geq 50\%$ reduction in MPN-SAF TSS from baseline will be summarized over time.

The maximum percent reduction from baseline in score across all post-baseline visits will be summarized. A waterfall plot of the maximum percent reduction in score, score at Cycle 4 Day 21 visit, and score at Cycle 7 Day 28 will be created.

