4.3.7. Other Assessments of Disease Response

The proportion of subjects with $\geq 35\%$ reduction in spleen size from baseline and $\geq 50\%$ reduction in score from baseline will be summarized over time. The proportion of subjects with an anemia response for MF patients and with erythroid response for CMML patients will also be summarized over time.

For patients who were transfusion-dependent at baseline, the number and percentage of patients who achieved transfusion independence following treatment start will be summarized for any 12-week period (at any time, at C4D21-12 weeks and C7D28-24 weeks). Transfusion dependency will be for pRBCs, platelets, and both, as defined in [Section 1.2.5.1](#). The rate of transfusions will also be summarized at any time post-baseline, from pre-baseline to baseline, from baseline to Week 12, and from Week 12 to Week 24.

For patients who were Red Blood Cell Transfusion Independent at Baseline, the number and percentage of patients becoming transfusion dependent following treatment start will be summarized for any 12-week period (at any time, at C4D21-12 weeks and C7D28-24 weeks). Transfusion dependency will be summarized pRBC as defined in Section 1.2.5.1.

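### CMML component response rates in SAP 4.3.1 have no response-eligible denominator, so patients who cannot meet a component's baseline threshold dilute them

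*SAP*

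**What the plan says.** The default denominator is in SAP 3.10, which says of categorical variables: "Percentages will be calculated from the total population, including patients with missing results". SAP 4.3 sets the efficacy population: "Efficacy analyses will be conducted using the mITT population for patients treated at" 12 µg/kg/day. Membership of that population (SAP 2.1) does not depend on eligibility for any response component.

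The component rates are in SAP 4.3.1: "For CMML patients, the number and percentage of patients who achieved erythroid, platelet, neutrophil, spleen or symptoms responses will also be presented". It refers to Section 8.2 for the criteria, and within that section only Table 8-4 defines these responses. Several need a qualifying baseline:

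- **Spleen:** palpable at more than 5 cm, or at least 10 cm for the 50% reduction route.
- **Symptom:** scores below 20 on the MPN-SAF TSS are not eligible.
- **Neutrophil:** at most 1.0 x 10^9/L.
- **Platelet:** at most 100 x 10^9/L, or a platelet transfusion requirement.
- **Erythroid, transfusion route:** at least 4 red cell transfusions in the preceding 8 weeks. The hemoglobin route has no baseline threshold.

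Elsewhere the SAP does restrict to patients at risk. In 4.3.5: "Spleen size by MRI/CT will be summarized over time for all patients with baseline splenomegaly". In 4.3.7: "For patients who were transfusion-dependent at baseline, the number and percentage of patients who achieved transfusion independence following treatment start". SAP 4.3.8.1 limits marrow-blast reduction to CMML patients with at least 5% blasts at baseline. By contrast, 4.3.6 says: "Symptom scores will be summarized over time for all patients". The first sentence of 4.3.7, on spleen reduction of at least 35% and score reduction of at least 50%, names no subset.

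**The concern.** For a patient whose baseline lies outside a component's threshold, non-response is fixed before the first infusion. Counting that patient in the denominator makes the percentage a product of two things: activity among those who could respond, and the share of the cohort that could respond. The exact interval required by SAP 3.2 then describes that product and not the response rate of interest.

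The component rates are central to Stage 3A. SAP 3.7 names evaluation of the individual components as its single primary efficacy endpoint, and SAP 3.1.2 sizes the stage within subsets that can respond, such as "approximately 8-10 patients with baseline splenomegaly" in each cohort of about 20. The sizing therefore uses one denominator and the component table another. SAP 3.5 also sets treatment-naïve beside relapsed/refractory patients, and those columns could differ through baseline case mix alone.

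**Working it through.** **Inputs.** Cohort size of about 20, with 8 to 10 splenomegaly patients (SAP 3.1.2). Worked example of a true rate of 0.15 with 10 patients evaluated (SAP 3.1.2). Two-sided 95% Clopper-Pearson intervals (SAP 3.2). July 2021 counts from protocol 14.2.1.

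**1. The plan's own figure.** P(at least 1 responder) = 1 − (1 − p)^N. With p = 0.15 and N = 10, 1 − 0.85^10 = 0.803, which reproduces the stated 80%. Here N counts patients evaluated for that response type, and the rule is a count, so no choice of percentage denominator changes it. (At N = 9 the value is 0.768 and at N = 8 it is 0.728, so the 80% belongs to the top of the 8 to 10 range.)

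**2. Dilution.** Expected percentage on the total = true rate among eligible x (eligible / total).

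| True rate among eligible | 8 of 20 eligible | 10 of 20 eligible |
|---|---|---|
| 15% | 0.15 x 0.40 = 6.0% | 0.15 x 0.50 = 7.5% |
| 30% | 12.0% | 15.0% |
| 50% | 20.0% | 25.0% |

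Two cohorts with the same true 50% rate but 8 and 10 eligible patients would thus read 20% and 25%.

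**3. Intervals (assumed outcomes).**

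- 4 responders, 8 of 20 eligible: 4/8 = 50% (15.7 to 84.3) among eligible; 4/20 = 20% (5.7 to 43.7) on the total.
- 3 responders, 10 of 20 eligible: 3/10 = 30% (6.7 to 65.2) among eligible; 3/20 = 15% (3.2 to 37.9) on the total.

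**4. Components with no planned eligible count.** For symptom, platelet and neutrophil response the documents give no eligible fraction. If it is assumed to lie between 10% and 75%, a true 50% rate reads between 0.5 x 0.10 = 5% and 0.5 x 0.75 = 37.5%.

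**5. Denominators in the protocol's own summary.** The sentence on spleen responses prints 42% twice. Fifteen responses is 42% only on all 36 patients (15/36 = 41.7%). Five responses is 42% only on the 12 with splenomegaly of at least 5 cm (5/12 = 41.7%, CI 15.2 to 72.3); on 36 it would be 5/36 = 13.9% (4.7 to 29.5). The five are reductions of at least 50%, which is not the Table 8-4 spleen definition, so this shows only how far the denominator matters.

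**6. Direction in 4.3.6 and 4.3.7.** These summaries use percentage reductions with no stated entry score. A patient scoring 0 cannot improve, but one with a low non-zero score can halve it through a trivial change. The gap is the same as in 4.3.1, but the bias need not be downward.

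**The case against.** The strongest reply is that the quoted sentence in SAP 3.10 is a missing-data rule. It keeps patients with missing results in the denominator, which is conservative and sound, and says nothing about ineligible patients. That stands: the fault is the silence of 4.3.1, which leaves 3.10 as the only stated default. A reader might infer that the sponsor deliberately chose to count ineligible patients; the documents do not show that.

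Symptom response has a partial answer too. Table 8-4's wording on scores below 20 can be read as removing those patients from the measure. Neither 4.3.1 nor 4.3.6 says so, and 4.3.6 refers to all patients. The table shells sit in a separate document (SAP 9) and may settle denominators; that cannot be checked here.

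Two stronger readings are tempting. The first is that every component rate is diluted, including transfusion independence and spleen volume. The documents contradict this: 4.3.5 and the transfusion summary in 4.3.7 are restricted, as is 4.3.8.1. The second is that a diluted rate would misdirect the choice of a Stage 3B endpoint. SAP 5 says that Stage 3A enrollment was not continued, Stage 3B will not start, and the correlative and Bayesian analyses are dropped. No such decision remains.

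Nor are the components beyond comparison. SAP 4.2 summarizes baseline spleen size, symptom score, transfusion dependence and platelets, and 4.3 provides by-patient listings, so eligible-only rates could largely be rebuilt. The all-patient rate is also a legitimate descriptive quantity. These points limit the harm, but a reader of the study report should not have to reconstruct its main component rates.

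**Conclusion.** The point holds for the 4.3.1 rates of palpable-spleen, symptom, platelet and neutrophil response, and for the transfusion routes inside erythroid and platelet response. The same omission affects 4.3.6 and the first sentence of 4.3.7. It does not hold for spleen volume (4.3.5), transfusion independence (4.3.7), marrow blasts (4.3.8.1), the hemoglobin route of erythroid response, or the at-least-one-responder rule.

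For spleen response at the planned case mix, the all-patient percentage is 0.40 to 0.50 of the eligible rate. This assumes that the planned 8 to 10 of 20 was achieved and that all of those patients meet the Table 8-4 threshold. SAP 3.1.2 counts splenomegaly from 5 cm while Table 8-4 requires more than 5 cm, and enrollment stopped early, so actual denominators may be smaller. The responder counts in the interval examples are assumed. The consequence is descriptive rates that understate activity among patients able to respond and vary with case mix; no remaining confirmatory decision depends on them.

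**What to change.** In SAP 4.3.1, present each component rate with its Clopper-Pearson interval among mITT patients who meet that component's Table 8-4 baseline threshold. Count eligible patients with missing follow-up as non-responders, and show the all-mITT percentage alongside. Report the transfusion routes of erythroid and platelet response separately, among patients transfusion-dependent at baseline for that product; the hemoglobin route can stay on all mITT patients.

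Apply the same rule to the 4.3.6 thresholds (entry score of at least 20) and to the first sentence of 4.3.7 (splenomegaly for the spleen part, the score threshold for the symptom part, both if the proportion is joint). Name one splenomegaly cut-off, since 4.3.5 gives none.

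No new data are needed: the change is one denominator column per component in the shells. The price is wider intervals on small denominators; in the 4-responder example the width goes from 43.7 − 5.7 = 38.0 to 84.3 − 15.7 = 68.6 percentage points. That width correctly reflects how few patients inform each rate.
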